2.5.3 Statistical hypothesis, model, and method of analysis**2.5.3.1 Primary endpoint**

The primary objective of the study is to evaluate superiority of QAW039 150 mg once daily over placebo (with SoC asthma therapy as the background therapy) by testing the following null hypothesis (H₀) versus the alternative hypothesis (H_a):

H₀: There is no difference in the change from baseline in pre-dose FEV₁ (L) at week 12 post-baseline for the patients treated with QAW039 150 mg once daily compared with placebo ($\mu_1 - \mu_2 = 0$)

H_a: There is a difference in the change from baseline in pre-dose FEV₁ (L) at week 12 post-baseline for the patients treated with QAW039 150 mg once daily compared with placebo ($\mu_1 - \mu_2 \neq 0$).

where;

μ_1 = Mean change from baseline in pre-dose FEV₁ (L) at week 12 of QAW039 150 mg once daily treatment;

μ_2 = Mean change from baseline in pre-dose FEV₁ (L) at week 12 of Placebo treatment;

The primary efficacy variable will be analyzed on the FAS using an analysis of covariance (ANCOVA) model with factors for treatment group, randomization strata [age group (<18 vs. ≥18 years), use or non-use of a second asthma controller medication at study entry, and region], as well as the baseline daytime asthma symptom score, baseline total daily SABA use and baseline pre-dose FEV₁ as continuous linear covariates. The variables contributing to the randomization strata (i.e. age group (<18 vs. ≥18 years), use or non-use of a second asthma controller medication at study entry, and region) are included separately in the model.

The least squares mean (“adjusted mean”) change from baseline for each treatment group, the difference in the least squares (LS) mean changes between the two treatment groups (QAW039 150 mg – placebo), and the two-sided 95% confidence interval along with the p-value for the difference will be obtained and combined from the primary analysis model through the multiple imputation approach described in [Section 2.5.4](#).

The superiority of QAW039 150 mg once daily to placebo as add on to SoC asthma therapy is established if the two-sided p-value is less than 0.05 and the 95% confidence intervals lie entirely to the right of 0 L.

Summary statistics for the primary endpoint

Summaries of observed absolute values and change from baseline in pre-dose FEV₁ (L) by treatment group and visit will be presented.

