The imputation and analysis will be implemented using the “five macros” available from www.missingdata.org.uk (for a full description see Carpenter et al (2013)). The first step in implementing this pattern mixture imputation approach is to fit a Bayesian Normal repeated measures model to estimate parameters from the observed on-study values (including on-treatment and off-treatment data). The model will include the same covariates as the primary model. Then use the estimated parameters to build possible predicted profiles for the unobserved values in a separate imputation model, one for each pattern of withdrawal. These profiles represent what we expect would happen to patients after they withdraw. Missing values for an individual are then imputed based on the profile of predicted means that matches their treatment, their time of withdrawal and other covariates. A large number of imputed datasets will be created, with their number chosen based on computational feasibility, but at least 1000. Observed and imputed data will be contrasted graphically. Each dataset will be analyzed using the model described in [Section 2.5.3.1](#) and the results will be combined using Rubin’s rule (Barnard and Rubin 1999) for final inference. A fuller description is given in the [Section 6.6.1](#) of the [Appendix](#).

Unless otherwise specified, for efficacy parameters, on-treatment data are defined as data on or after the first day of treatment with double-blind medication, but before or on the day of the last day of treatment with double-blind study medication; on-study data are defined as data on or after the first day of treatment with double-blind medication, but before or on the day of the last day of treatment period.

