2.6.3 AQLQ+12

The 32 items in the AQLQ+12 are divided into 4 domain-specific scores and a total score as follows:

- Symptoms = Mean of Items 6, 8, 10, 12, 14, 16, 18, 20, 22, 24, 29, 30 (12 items)
- Activity limitation = Mean of Items 1, 2, 3, 4, 5, 11, 19, 25, 28, 31, 32 (11 items)
- Emotional function = Mean of Items 7, 13, 15, 21, 27 (5 items)
- Environmental Stimuli = Mean of Items 9, 17, 23, 26 (4 items)
- Overall Score = Mean of Items 1 to 32 (32 items)

Each item of the AQLQ+12 is equally weighted and scored along a 7-point scale, where 1 indicates maximal impairment and 7 indicates no impairment. Thus, higher scores indicate better asthma-related HRQOL (Health-Related Quality of Life). There is a mean score calculated for each of the four domains, as well as an overall quality-of-life score, which is the mean score of all 32 items. The resultant overall scores will be between 1 and 7.

The developer suggests no more than 10% of missing data. This means no more than 3 missing responses for the overall score and no more than 1 missing response per domain. For the

symptoms and activity domain scores, one missing value per domain is allowed. For the emotional function and environmental stimuli domain scores, no missing values are allowed. If these limits for missing questions are exceeded, the variable will be considered missing and will be imputed as described in [Section 2.6.4](#).

The minimal important difference (MID), defined as “the smallest difference in score which patients perceive as beneficial and would mandate, in the absence of troublesome side effects and excessive cost, a change in the patient’s management,” of 0.5 has been established for this questionnaire as clinically significant ([Juniper, et al 1994](#)).

The change from baseline in AQLQ+12 at week 12 will be analyzed using an ANCOVA model in a similar fashion as the primary efficacy variable, based on on-study data (including on-treatment and off-treatment data). The model will include factors for treatment group, age group (<18 vs. ≥18 years), use or non-use of a second asthma controller medication at study entry, and region, as well as the baseline daytime asthma symptom score, baseline total daily SABA use, baseline pre-dose FEV₁, and baseline AQLQ as continuous linear covariates.

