The least squares mean (“adjusted mean”) change from baseline for each treatment group, the difference in the least squares mean changes between the two treatment groups (QAW039 150 mg – placebo), and the two-sided 95% confidence interval along with the superiority p-value for the difference will be obtained. This model will be fitted to each of multiple imputations generated using the same approach as for the primary analysis.

In addition, the mean of change from baseline in AQLQ +12 at Week12 will be analyzed based on on-treatment data using a MMRM model in which treatment, age group (<18 vs. ≥18 years), use or non-use of a second asthma controller medication at study entry, region, visit and treatment-by-visit interaction will be included as fixed-effect factors, and baseline pre-dose FEV₁ value as well as the baseline daytime asthma symptom score, baseline total daily SABA use, baseline AQLQ and visit-by- baseline AQLQ as covariates. A common unstructured covariance matrix among visits for each treatment group will be used. The analysis will be performed based on all available on-treatment data up to week 12. The estimated treatment differences for all treatment comparisons will be tabulated along with the associated 95% confidence intervals and their two-sided p-values.

Summaries of absolute values and change from baseline will be presented by visit and by treatment group based on on-treatment data.

In addition, the proportion of patients with a change from baseline (improvement) in AQLQ+12 score of at least +0.5 unit based on on-treatment data will be analyzed using logistic regression by visit. The model will include treatment, age group (<18 vs. ≥18 years), use or non-use of a second asthma controller medication at study entry and region as a fixed class effects, and the baseline AQLQ+12 as continuous linear covariates. Estimates of the odds ratios between QAW039 group and placebo will be displayed along with associated 95% confidence intervals and two-sided p-values by visit.

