2.6.4 Handling of missing values/censoring/discontinuations

Handling of missing daytime asthma symptom scores and total daily SABA use

The weekly mean will be calculated based on the non-missing post-baseline assessments as long as there are at least 4 days with non-missing data in a one-week period. Otherwise, the weekly mean will be set to missing. The multiple imputations will be carried out on the weekly mean data using J2R approach in a similar fashion as primary analysis described in [Section 2.5.4](#). The completed weekly mean data after imputation will be used in the model to calculate the mean of change from baseline over 12 weeks of treatment.

Handling of missing AQLQ+12 values

The missing data of AQLQ+12 will be imputed using the same approach as primary analysis described in [Section 2.5.4](#).

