6.6.1 Multiple imputations for primary and secondary variables

The imputation and analysis of primary and secondary variables will be implemented using the “five macros” available from www.missingdata.org.uk (for a full description see Carpenter et al (2013)). The purpose and activities of each of the five macros is described below.

Part1A declares the parameter estimation model and checks consistency with the input dataset. It builds a master dataset which holds details of the current job and also builds indexes for the classification variables, which may be either numeric or character.

Part1B fits the parameter estimation model using the MCMC procedure and draws a pseudo-independent sample from the joint posterior distribution for the linear predictor parameters and the covariance parameters.

Part2A calculates the predicted mean under MAR, and under MNAR for each subject based on their withdrawal pattern once for each draw of the linear predictor parameter estimates. The choice of MNAR is controlled by the method used, which may vary from subject to subject.

Part2B imputes the intermediate missing values using MAR and the trailing missing values using MNAR, by deriving the conditional distribution for the missing values conditional on the observed values and covariates, using the appropriate sampled covariance parameter estimates.

Part3 carries out a univariate ANOVA analysis at selected time points usually based on the same covariates as the parameter estimation model. It then combines the least-squares means and their differences using the MIANALYZE procedure to provide final results.

This is example code to implement the primary analysis:

```
%part1A(Jobname=fev1
,Data=RE
,Subject=subjid
,Response=aval
,Time=visit
,Treat=trt01pn
,Covbytime= basefev basescore basesaba
,Catcov=stratum
,
);
```

Where subjid = subject identifier

aval = change from baseline in FEV1 value at visit during the treatment epoch

visit = treatment period visit number

trt01pn = planned treatment

basefev = baseline FEV1 value

basescore = baseline daytime asthma symptom score

basesaba = baseline total daily SABA use

stratum = randomization strata (patient age (<18 years or \geq 18 years), use or not use a second asthma controller at study entry, region)

```
%part1B(Jobname=fev1
,Ndraws=1000
,thin=750
,seed=12345
);
%part2A(Jobname=fev1_J2R
,inname=fev1
,methodV=Mymethod
,refV=Myreference
);
```

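### As written, the SAP imputes missing AQLQ+12 change without baseline AQLQ, although the AQLQ+12 analysis model adjusts for it; the effect is small and one sentence in SAP 2.6.4 would remove it

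*SAP*

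**What the plan says.** SAP 2.5.4 describes a Bayesian repeated-measures model for jump-to-reference (J2R) imputation and sets its covariates: "The model will include the same covariates as the primary model". The primary model in SAP 2.5.3.1 has treatment, age group, second controller and region as factors. Its continuous terms are baseline symptom score, "baseline total daily SABA use and baseline pre-dose FEV₁ as continuous linear covariates". Baseline AQLQ is not among them.

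For AQLQ+12, SAP 2.6.3 lists the same terms "and baseline AQLQ as continuous linear covariates". Its MMRM and responder models also include baseline AQLQ. On imputation, SAP 2.6.3 says "This model will be fitted to each of multiple imputations generated using the same approach as for the primary analysis". SAP 2.6.4 says "The missing data of AQLQ+12 will be imputed using the same approach as primary analysis described in" Section 2.5.4. Neither section adds a covariate to the imputation step, and Protocol 9.5.1.3 does not either.

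SAP 6.6.1 is titled for primary and secondary variables, but its only macro call lists "Covbytime= basefev basescore basesaba" and is introduced with "This is example code to implement the primary analysis". It adds that the final ANOVA step is "usually based on the same covariates as the parameter estimation model".

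**The concern.** The imputed quantity is change from baseline, which normally depends on the baseline of the same scale. An imputation model that leaves out a covariate of the analysis model draws values that are unrelated to that covariate, given everything else in the model. When those values are then analysed with the covariate included, its slope is attenuated and residual variance rises. If missingness depends on the covariate differently by arm, the treatment difference also shifts.

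AQLQ+12 is tested as H4 under familywise error control. It is measured at only one scheduled visit between baseline and Week 12 (Week 4), so fewer observed values can stand in for the baseline than for FEV1. At stake are a little precision and a possible small bias in H4. There is also a reproducibility problem: one programmer could follow the covariate sentence literally and another could match the analysis model, and they would get different H4 results from the same SAP.

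**Working it through.** **Step 1. Covariates side by side.**

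| Endpoint | Own baseline in the primary covariate list (SAP 2.5.3.1) | Own baseline in its analysis model |
|---|---|---|
| FEV1 | yes | yes |
| Daytime symptoms | yes | yes |
| SABA use | yes | yes |
| AQLQ+12 | **no** | **yes** |

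The mismatch is confined to AQLQ+12.

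**Step 2. The plan's own figure.** SAP Section 3 gives 325 per arm, effect 0.5 in patients who stay on treatment, SD 1, 15% discontinuing with half of them completing, and 98% power at the local level 0.02 x 0.05 = 0.001.

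- Missing at Week 12: 0.15 x 0.5 = 7.5%, about 49 of 650 patients.
- Diluted effect, assuming that discontinuers carry none: 0.5 x (1 - 0.15) = 0.425.
- SE = sqrt(2/325) = 0.0784, and 0.425/0.0784 = 5.42.
- Power = Phi(5.42 - 3.29) = 98.3%, against the stated 98%.

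**Step 3. Simulation with and without baseline AQLQ in the imputation model.** There were 600 trials per scenario, 30 imputations, J2R for QAW039, MAR for placebo and Rubin's rules. The analysis model always contained baseline AQLQ. The documents give no AQLQ+12 correlations, so these inputs are assumptions:

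- correlation rho of 0.3, 0.5 or 0.7 between scores at baseline, Week 4 and Week 12, with change SD fixed at 1;
- one proxy baseline covariate correlated 0 or 0.5 with baseline AQLQ;
- half of discontinuations before Week 4;
- where dropout depends on baseline AQLQ, a log-odds of 0.7 per SD.

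Shift means the estimate without baseline AQLQ minus the estimate with it. Paired entries are for proxy correlation 0 and 0.5.

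| | rho 0.3 | rho 0.5 | rho 0.7 |
|---|---|---|---|
| SE without (dropout unrelated to baseline) | 0.0693 / 0.0687 | 0.0731 / 0.0727 | 0.0767 / 0.0765 |
| SE with | 0.0665 / 0.0665 | 0.0713 / 0.0713 | 0.0757 / 0.0757 |
| SE increase | 4.2% / 3.3% | 2.5% / 2.0% | 1.3% / 1.1% |
| Shift, dropout unrelated | 0.0023 / 0.0024 | 0.0016 / 0.0017 | 0.0007 / 0.0007 |
| Shift, related equally in both arms | 0.0028 / 0.0029 | 0.0016 / 0.0018 | 0.0015 / 0.0014 |
| Shift, related in QAW039 arm only | -0.0151 / -0.0111 | -0.0131 / -0.0096 | -0.0097 / -0.0071 |
| Shift, opposite directions by arm | -0.0324 / -0.0245 | -0.0275 / -0.0207 | -0.0214 / -0.0161 |

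The Monte Carlo error of each mean estimate is 0.0024-0.0031, so the shifts in the two equal-dropout rows cannot be told from zero. With baseline AQLQ included, the estimate is 0.422-0.427 in every scenario, against a target of 0.425. Without it, the baseline slope is attenuated by about 5-7%. Simulated power at 0.001 is 97.7-100% without baseline AQLQ and 98.3-100% with it.

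**Step 4. Checks under other assumptions.**

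- Baseline-change correlation -0.45, Week 4 to Week 12 correlation 0.65, proxy at -0.5: SE 0.0736 without against 0.0726 with (+1.4%).
- Same set-up, opposite-direction dropout: 0.4031 - 0.4237 = -0.021. At 25% discontinuation: 0.3533 - 0.3815 = -0.028.
- Reversing the two arms' dropout directions reverses the sign: -0.017 becomes +0.018. With no true effect, the shift can be +0.017, a small spurious benefit.

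**The case against.** The strongest case against is that the covariate sentence sits in the FEV1 section and may mean only that imputation and analysis should share covariates. SAP 2.5.4 cannot carry over to AQLQ+12 word for word, since it also averages two spirometry readings and sends each dataset to the FEV1 ANCOVA. Some adaptation is needed, and matching the AQLQ+12 analysis model is the natural one. SAP 6.6.1 points the same way, and SAP 6.6 places the code in TFL shells that are not available here. So the authors may have intended to include baseline AQLQ. What remains is that no sentence says so. SAP 2.6.3 overrides the analysis model for AQLQ+12, but nothing overrides the imputation covariates.

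A reader might infer that the macro call in SAP 6.6.1 confirms the omission. It does not: it is an FEV1 example and does not settle the AQLQ+12 call.

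A reader might also infer that a patient who leaves before Week 4 is imputed with no AQLQ-related information. That goes too far. Protocol Table 6-1 schedules AQLQ+12 at the treatment discontinuation visit, and SAP 6.3 lets that visit stand in for a missed scheduled visit to which it is closest. Baseline symptom score is a partial proxy, and an observed Week 4 change carries some of the baseline. The cover is incomplete. Counting all clinic visits, the midpoints are (14+28)/2 = Day 21, (28+56)/2 = Day 42 and (56+84)/2 = Day 70. A discontinuation visit before Day 21, or between Days 42 and 70, is therefore not closest to a visit with a scheduled AQLQ+12. The simulations did not model this remapping.

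Finally, the supportive AQLQ+12 MMRM does condition on baseline AQLQ. It uses on-treatment data only, so it addresses a different estimand and is only a partial check.

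**Conclusion.** The mismatch holds on a literal reading: for one alpha-controlled endpoint, the imputation model is poorer than the analysis model. Severity is low.

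At about 7.5% missing, the SE is roughly 1-4% larger. There is no material bias when dropout is unrelated to baseline AQLQ or related to it equally in both arms. When the relation differs by arm, the shift is about 0.01-0.03 points in either direction. The largest, 0.032, is about 6% of the 0.5 minimal important difference and just under half an SE (0.0324/0.0693 = 0.47).

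A reader might infer that H4 or its stated power is in danger. The documents do not support that: the 98% reproduces, and simulated power stays at about 98-100% either way. Nor do they suggest that dropout would relate to baseline AQLQ differently in the two arms. The sizes rest on the assumed correlations, proxy strength, dropout timing and dropout relation listed above.

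**What to change.** State in SAP 2.6.4 that the AQLQ+12 imputation model uses the covariates of the SAP 2.6.3 AQLQ+12 analysis model. In practice, add baseline AQLQ+12 to Covbytime in the %part1A call for this endpoint. The cost is one sentence and one variable that is already collected at Visit 199. There is no evident downside, and no stated power figure needs revising. It should be settled before unblinding so that only one H4 result can follow from the SAP.

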2.5.5 Supportive analyses

Sensitivity analysis

Two-dimensional tipping point analysis will be performed corresponding to the primary analysis on the FAS. Missing data after study treatment discontinuation will be firstly imputed in the same way as for the primary analysis. Then it will be explored by how much the imputed continuous missing data for the QAW039 treatment and the placebo arms would have had to change compared to the imputation values in the primary analysis in order to overturn conclusions from the primary analysis. After such tipping point(s) is determined, clinical judgment can be applied as to the plausibility of the assumptions underlying this tipping point. This methodology will provide a good picture of what it would take to overturn study conclusions based on varying assumptions about missing data.

Supplementary analysis

The primary efficacy variable will also be analyzed using a repeated measures (MMRM) analysis model in which treatment, age group (<18 vs. ≥18 years), use or non-use of a second asthma controller medication at study entry, region, visit and treatment-by-visit interaction will be included as fixed-effect factors, and baseline pre-dose FEV₁ value as well as the baseline daytime asthma symptom score, baseline total daily SABA use and visit-by-baseline FEV₁ as covariates. A common unstructured covariance matrix among visits for each treatment group will be used. If this model does not converge, a heterogeneous AR (1) covariance structure will be used. If this model still does not converge, a heterogeneous compound symmetry covariance structure will be used. The analysis will be performed based on all available on-treatment data up to week 12 and based on a likelihood method with an assumption of MAR for missing data assuming a hypothetical situation of continued treatment. On-treatment data is defined as all available data collected while patients took the study drug up to the week 12 visit. The estimated treatment differences for all treatment comparisons will be tabulated along with the associated 95% confidence intervals and their two-sided p-values.

Rank-based analysis

In a further rank-based supportive analysis for the primary endpoint, patients will be ranked from largest to smallest in the following sequence with high ranks denoting greater efficacy.

1. patients who completed the trial
2. patients who withdrew from the trial and did not die
3. patients who died

Note: death refers to adverse events with fatal outcome on-study.

Within category 1, patients with higher change from baseline FEV₁ at Week 12 will be ranked greater than patients with lower change from baseline. Patients who completed the trial with missing FEV₁ data at Week 12 will be ranked lower than anyone who completed the trial with non-missing FEV₁ data at Week 12. Within that, patients with higher change from baseline in FEV₁ at a later visit will get higher ranks. In case of ties in the visits with last available FEV₁ data, patients with higher change from baseline in FEV₁ are assigned a higher rank. In case of ties in the FEV₁ values, midranks will be used.

Within categories 2 and 3, patients that withdraw from the trial later will get higher ranks than patients that withdraw early. In cases in which patients withdraw at same study day, patients with higher change from baseline in FEV₁ at a later visit will get higher ranks. In case of ties in the FEV₁ values or no available post-baseline assessments of the primary variable, midranks will be used.

A Wilcoxon rank-sum test (Van Elteren test) stratified by age group (<18 vs. ≥18 years), use or non-use of a second asthma controller medication, and region will be used to analyze the ranked data.

Per-protocol analysis

The primary analysis may be repeated for the PPS.

